- For Grade 2 or Grade 3 ITP, withhold ezabenlimab and BI 836880 and initiate systemic therapy. ezabenlimab and BI 836880 may be restarted upon resolution to at least grade 1.
- For Grade 4 ITP, permanently discontinue ezabenlimab and BI 836880.

Infusion related reactions (IRRs):

[figure not shown]
- Signs and symptoms of IRRs usually develop during or shortly after ezabenlimab infusion and generally resolve completely within 24 hours of completion of infusion. If symptoms develop during infusion, they may be managed with slowing or transient interruption of infusion.

Please refer to [Section 5.2.7](#) for more details about infusion related reactions.

[figure not shown]

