- For Grade 3 irAEs, ezabenlimab and BI 836880 has to be withheld, and treatment with high-dose corticosteroids (1-2mg/kg/d) is usually warranted. Upon improvement, steroids should be tapered over 4-6 weeks. Non-steroidal immunosuppressives (e.g. infliximab, mycophenolate mofetil) should be considered if no improvement or worsening occurs within the initial 48 to 72 hours. Upon recovery to grade 1 or less, and on corticosteroid \leq 10 mg per day, restarting of ezabenlimab and BI 836880 may be considered for selected irAEs, but caution is advised, in particular in patients with early-onset irAEs. Expert consultancy is recommended prior to restart of therapy.
- Most Grade 4 irAEs warrant permanent discontinuation of ezabenlimab and BI 836880.
- Restart of therapy is commonly possible for endocrine irAEs regardless of grade once stable hormone replacement has been instituted and symptoms have recovered. In case of multiple hormone deficiencies, corticosteroid replacement has to precede thyroid hormone replacement therapy by several days in order to avoid adrenal crisis.
- A dose reduction of BI 836880 may be considered, but is not required for the first occurrence of an endocrine irAE.

In case of prolonged steroid therapy or treatment with immunosuppressive consider the possibility of opportunistic infections and tuberculosis reactivation, administer prophylactic antibiotics where appropriate.

Commonly, referral to experts in the management of organ-specific conditions is highly recommended, especially for irAEs grade 3 or grade 4, or irAEs where management is complex.

Ezabenlimab and BI 836880 should be permanently discontinued for immune related:

- encephalitis, aseptic meningitis, transverse myelitis, or Guillain-Barre syndrome of any grade
- acquired thrombotic thrombocytopenic purpura of any grade
- myocarditis of any grade
- myasthenia gravis, peripheral neuropathy or autonomic neuropathy of grade ≥ 3
- myositis grade 2 with objective findings (see below), any myositis grade ≥ 3
- hepatitis grade ≥ 3 (transaminase >5 times ULN [or >10 times ULN if baseline was $>2.5-5$ times ULN] or total bilirubin >3 times ULN [or >5 times ULN if baseline was $>1.5-3$ times ULN], recurrent hepatitis grade ≥ 2)
- nephritis grade ≥ 3 , persisting grade 2 nephritis unresponsive to initial steroid therapy or worsening, and recurrent nephritis grade ≥ 2
- pneumonitis grade ≥ 3 ,

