- rash, bullous dermatoses, severe cutaneous adverse reaction, Stevens Johnson Syndrome, toxic epidermal necrolysis of grade 4, and recurrent rash grade ≥ 3
- colitis grade 4, and recurrent colitis of any grade
- uveitis, iritis, episcleritis of grade ≥ 3
- autoimmune-hemolytic anemia grade ≥ 2
- haemolytic uremic syndrome grade ≥ 3
- immune thrombocytopenia grade 4
- any recurrent irAE grade ≥ 3 ,
- inability to taper steroids to 10 mg or less prednisone or equivalent within 12 weeks, or persistent Grade 2-3 AEs that do not recover to Grade 1 or less within 12 weeks.

For BI 836880, up to 1 dose reductions are allowed if the treatment pause due to an AE. Dose adjustment of ezabenlimab besides interrupting of both compounds or permanently discontinuing ezabenlimab are not allowed (see [Section 4.1.4](#)).

Pneumonitis:

- For Grade 1 pneumonitis with radiographic evidence of worsening, withhold ezabenlimab and BI 836880 until improvement or resolution; ezabenlimab and BI 836880 may be reintroduced upon radiographic improvement. In the absence of radiographic improvement within 3-4 weeks, follow guidance as for grade 2 event.
- For Grade 2 pneumonitis, hold ezabenlimab and BI 836880 until resolution to at least grade 1. If not already started, initiate therapy for the event as per available guidelines. Follow guidance as for grade 3 pneumonitis if no clinical improvement after 48 -72 hr of starting therapy.
- For Grade 3-4 pneumonitis, permanently discontinue ezabenlimab and BI 836880 and immediately initiate treatment according to available guidelines.

Diarrhoea/Colitis:

- For Grade 1 diarrhoea/colitis, consider interruption of ezabenlimab and BI 836880 therapy.

Proprietary confidential information © 2023 Boehringer Ingelheim International GmbH or one or more of its affiliated companies

- For Grade 2 diarrhea/colitis, withhold ezabenlimab and BI 836880 until patient's symptoms recovered to grade 1 or less. Consider initiating treatment with steroids.
- For Grade 3 diarrhoea/colitis, withhold ezabenlimab and BI 836880 and immediately start treatment (steroids, non-steroidal immunosuppressants) as per available guidelines.
- For Grade 4 diarrhoea/colitis, permanently discontinue ezabenlimab and BI 836880 and immediately commence adequate therapy (e.g. i.v. corticosteroids).

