- For Grade 1-3 colitis, restart of ezabenlimab and BI 836880 may be considered once symptoms improve to Grade 1 or less without need for continued steroids. After careful benefit risk assessment, ezabenlimab and BI 836880 may also be restarted after recovery to grade 1 or less, and on corticosteroid ≤ 10 mg per day
- Ezabenlimab and BI 836880 should be permanently discontinued for recurrent diarrhoea/colitis of any grade.

Diabetes

- Consider withholding ezabenlimab and BI 836880 in case of grade 2 hyperglycemia.
- Check for ketonuria. In case of new onset of diabetes or unexpected worsening of preexisting diabetes, check for new manifestation of type 1 diabetes.
- For new onset Type 1 diabetes mellitus, or Grade 3-4 hyperglycaemia associated with ketosis (ketonuria or metabolic acidosis)
 - Initiate insulin therapy
 - Evaluate subjects as appropriate per available guidelines regarding presence of type 1 diabetes
 - Ezabenlimab and BI 836880 should be withheld until glucose level is controlled with insulin with no sign of ketoacidosis.
- Ezabenlimab and BI 836880 may be restarted once insulin therapy has established stable glycemic control.

Thyroid disorders:

Thyroid disorders can occur at any time during treatment. Monitor subjects for changes in thyroid function (at screening and in regular intervals during treatment as indicated in [Flow Chart](#) (safety lab) and [Section 5.2.3](#), and as indicated based on clinical evaluation) and for clinical signs and symptoms of thyroid disorders. For diagnosed thyroid disorders, thyroid hormone supplementation and monitoring should occur as per available guidelines.

- Primary hypothyroidism:
 - For Grade 1 hypothyroidism, ezabenlimab and BI 836880 may be continued, with regular monitoring of thyroid values.
 - For Grade 2 hypothyroidism, consider withholding ezabenlimab and BI 836880
 - For Grade 3-4 hypothyroidism, withhold ezabenlimab and BI 836880, consider admission and IV therapy, especially in case of myxedema
 - Ezabenlimab and BI 836880 may be restarted once symptoms resolve to baseline with appropriate thyroid hormone supplementation

Proprietary confidential information © 2023 Boehringer Ingelheim International GmbH or one or more of its affiliated companies

- Primary hyperthyroidism:
 - For Grade 1 hyperthyroidism, ezabenlimab and BI 836880 may be continued, with regular monitoring of thyroid values.

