 - For Grade 2 hyperthyroidism, consider withholding ezabenlimab and BI 836880, initiate therapy as per available guidelines.
 - For Grade 3-4 hyperthyroidism, withhold ezabenlimab and BI 836880. Consider hospitalization, especially in case of Thyrotoxicosis.
 - Ezabenlimab and BI 836880 may be restarted once symptoms resolve to baseline.
Note: in case of concomitant adrenal dysfunction, this must be corrected first, prior to thyroid hormone replacement (reduced stress tolerance)

Adrenal insufficiency

- Interruption of ezabenlimab and BI 836880 therapy should be considered for adrenal insufficiency grade 1 or 2, and is warranted for grade 3 and grade 4 adrenal insufficiency, until patient is stabilized on hormone replacement therapy.
- Therapy with ezabenlimab and BI 836880 may be restarted once stable replacement therapy has been achieved.
- Note: in case of concomitant hypothyroidism, steroid replacement therapy should precede thyroid hormone substitution to avoid adrenal crisis.

Hypophysitis

- Diagnostic workup for hypophysitis should be considered e.g. for patients with multiple endocrinopathies, unexplained fatigue, new severe headaches or vision changes.
- Patients should be appropriately advised regarding potentially reduced stress tolerance and increased substitution demands e.g. in case of infections, and to wear a medical alert bracelet to inform medical personnel about potentially increased hormone demands in situations of stress, in case of emergencies.
- Interruption of ezabenlimab and BI 836880 therapy should be considered for Grade 1 or 2 hypophysitis, and is warranted for Grade 3 and higher hypophysitis, until patient is stabilized on hormone replacement therapy.

Hepatitis

- Work-up for other causes of elevated liver enzymes, see also section on potential DILI ([Section 5.2.7](#)).
- For Grade 1 hepatitis (elevated AST/ALT $< 3 \times$ ULN and/or total bilirubin $< 1.5 \times$ ULN), ezabenlimab and BI 836880 may be continued, close monitoring of liver values is warranted.
- For Grade 2 hepatitis (AST/ALT 3–5 \times ULN and/or total bilirubin > 1.5 to $\leq 3 \times$ ULN), ezabenlimab and BI 836880 should be suspended. Monitoring of liver values every 3 days is recommended. Initiate treatment according to available guidelines. Restarting of ezabenlimab and 836880 may be considered upon recovery to grade 1 or less, and on corticosteroid ≤ 10 mg per day.

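### Appendix 10.4's 12-week permanent-stop item has no endocrine exception and contradicts the endocrine restart rules in the same appendix

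*Protocol*

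**What the plan says.** All the text at issue is in Protocol Appendix 10.4.

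**Stop rule.** The list opens "Ezabenlimab and BI 836880 should be permanently discontinued for immune related". The second half of its final bullet is "persistent Grade 2-3 AEs that do not recover to Grade 1 or less within 12 weeks". Neither the opening line nor the item excludes any organ class.

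**Endocrine restart rules.**
- General rule: "Restart of therapy is commonly possible for endocrine irAEs regardless of grade once stable hormone replacement has been instituted and symptoms have recovered".
- Adrenal insufficiency: "Therapy with ezabenlimab and BI 836880 may be restarted once stable replacement therapy has been achieved".
- Hypophysitis: interruption "is warranted for Grade 3 and higher hypophysitis, until patient is stabilized on hormone replacement therapy". There is no separate restart sentence.
- Diabetes: both drugs "should be withheld until glucose level is controlled with insulin with no sign of ketoacidosis", and then "Ezabenlimab and BI 836880 may be restarted once insulin therapy has established stable glycemic control".
- Primary hypothyroidism: both drugs "may be restarted once symptoms resolve to baseline with appropriate thyroid hormone supplementation". Primary hyperthyroidism has the same symptom condition without the supplementation.

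For Grade 2 adrenal insufficiency, hypophysitis, hypothyroidism and hyperthyroidism, the appendix asks the investigator only to consider an interruption.

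**The concern.** The general Grade 2 and Grade 3 rules in Appendix 10.4 tie restart to recovery to Grade 1 or less. The endocrine rules depart from that and replace the grade test with control of the disorder. The stop list brings the grade test back at week 12 without repeating the endocrine departure.

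Read literally, the list takes both drugs away permanently from patients whom the endocrine rules would allow to continue. Sites could also resolve the contradiction differently. Two things are affected: time on treatment, and the count of drug-related adverse events leading to discontinuation, which is a secondary endpoint (Section 2.1.3). Section 7.2 plans no formal hypothesis testing, so no error rate is involved.

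Patients taken off drug without progression are followed under Section 6.2.5.1, but that follow-up also ends when a new anti-cancer therapy starts. Observation to progression is therefore not guaranteed after such a stop.

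**Working it through.** The plan states no figure on this point, so the check compares the rules and then gives a rough scale.

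**1. The rules side by side**, for an endocrine event still Grade 2-3 at week 12:

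| Disorder | Condition in its own rule | Grade or time limit in that rule | Own rule if the condition is met | 12-week item |
|---|---|---|---|---|
| Adrenal insufficiency | Stable replacement | None | Restart allowed | Permanent stop |
| Hypophysitis | Stabilised on replacement | None | Interruption ends | Permanent stop |
| Diabetes | Glycaemic control on insulin, no ketoacidosis | None | Restart allowed | Permanent stop |
| Hypothyroidism | Symptoms back to baseline on hormone | None | Restart allowed | Permanent stop |
| Hyperthyroidism | Symptoms back to baseline | None | Restart allowed | Permanent stop |
| General endocrine rule | Stable replacement and symptoms recovered | Any grade, no limit | Restart commonly possible | Permanent stop |

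The conflict is clearest in the first three rows, whose own conditions do not require symptoms in general to resolve. It is narrower in the last three, where symptoms must have gone but the recorded grade is still not a condition. Events already at Grade 1 or less are unaffected.

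**2. Can the case arise?** The DLT table in Section 5.2.6.1 exempts Grade 3 endocrine disorders that are asymptomatic and managed with or without steroids or hormone replacement. The protocol itself therefore recognises an endocrine event that carries Grade 3 without symptoms while under treatment.

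**3. Does anything set precedence?** No sentence in Appendix 10.4 does. In Section 4.1.4, the Part 2 re-administration criteria leave further treatment to the investigator and the Clinical Monitor, but this concerns re-dosing in general and does not override a permanent-stop item. The paragraph on treatment delay in the same section speaks of restart after resolution to Grade 1 or baseline. It has no endocrine exception either, so it does not settle the matter.

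**4. Scale.** Inputs:
- 44 patients on treatment in January 2022 (Section 1.1).
- 59 of 359 patients with an immune-related event in the pooled combination trials, any organ and any grade (Section 1.2.1).
- Assumed, because the protocol gives neither: the share of these events that are endocrine, 10% to 50%; and the share of those still Grade 2-3 at week 12, 10% to 50%.

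Results:
- Any immune-related event: 44 × 59/359 = 7.23.
- Endocrine: 7.23 × 0.10 = 0.72, to 7.23 × 0.50 = 3.6.
- Still Grade 2-3 at week 12: 0.72 × 0.10 = 0.07, to 3.6 × 0.50 = 1.8.

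That is about 0 to 2 patients.

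**The case against.** The strongest reply is that the endocrine exception already exists. The general endocrine bullet removes grade as the test, dedicated sections follow for each disorder, and specific rules are naturally read as governing over a catch-all at the end of a list. The appendix also says it gives only limited guidance and refers sites to published guidelines. That reading is sensible and is probably what was intended, but the text does not state it. The stop item is worded as what should be done, the restart rules as what may be done, so a cautious site could fairly follow the stop item. Limited guidance excuses brevity, not opposite instructions.

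A second reply is that the general endocrine bullet covers every endocrine event and also requires symptoms to have recovered, which narrows the adrenal and hypophysitis cases. That is right, and it narrows the conflict without removing it, because recovered symptoms are not the same as a recorded Grade 1.

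Third, the DLT exemption concerns the first three-week cycle and does not show that a grade persists to week 12. CTCAE definitions are not in the document, so how often this happens is unknown. That stands, and it is why the size is given only as a range under assumptions. The base is rough too: 59/359 is a pooled any-organ proportion applied to patients already on treatment.

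Fourth, the follow-up rule in Section 6.2.5.1 applies to every patient who stops without progression. This also stands. It describes a consequence of an avoidable stop and is not a separate fault of the 12-week item.

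**Conclusion.** The contradiction is real and the point is minor. For an endocrine event that meets its own restart condition but remains Grade 2-3 at week 12, Appendix 10.4 both allows restart and calls for permanent discontinuation, with no rule of precedence.

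The number of patients affected is probably small. Recruitment has stopped (Section 3.2), supply of the combination ends on 30 April 2025 (Section 4.1.4), and the estimate of about 0 to 2 patients rests on two assumed shares and a pooled rate used only for scale. No response or dose-finding result is shown to change. For a patient who is affected, the stake is permanent loss of both drugs.

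**What to change.** In the final bullet of the permanent-discontinuation list in Appendix 10.4, extend the item to read: "persistent Grade 2-3 AEs that do not recover to Grade 1 or less within 12 weeks", *except endocrine irAEs that meet the restart condition given for that disorder in this appendix*. Add a cross-reference to it from the general endocrine restart bullet.

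The clause uses the conditions already written for each disorder and adds none, so it fits adrenal insufficiency, hypophysitis, diabetes and both thyroid disorders as they stand. The 12-week stop remains in force for every other organ.

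The cost is one clause and one cross-reference, with no extra patients or procedures. The same amendment could check two neighbouring texts that also lack an endocrine exception: the treatment-delay paragraph in Section 4.1.4, and the list item on recurrent events of Grade 3 or higher. The conflict described here does not depend on either.

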- For Grade 3 or higher hepatitis, ezabenlimab and BI 836880 has to be permanently discontinued. Immediately initiate treatment as per guidelines.

For eligible patients with elevated screening/baseline AST/ALT (>2.5-5x ULN or bilirubin >1.5-3x ULN):

- Carefully monitor patients for signs of autoimmune hepatitis.
- In case of increased levels of AST/ALT >2x baseline to ≤10x ULN and/or bilirubin >2x baseline to ≤5x ULN, ezabenlimab and BI 836880 should be suspended. Monitoring of liver values every 3 days or more frequently, if clinically indicated, is recommended. Restarting of ezabenlimab and BI 836880 may be considered upon recovery to baseline or less, and on corticosteroid ≤ 10 mg per day.
- In case of increased AST/ALT >10x ULN and/or bilirubin >5x ULN, ezabenlimab and BI 836880 have to be permanently discontinued. Initiate treatment as per guidelines.

Nephritis

- For Grade 1 nephritis, consider temporarily withholding ezabenlimab and BI 836880.
- For Grade 2 nephritis, withhold ezabenlimab and BI 836880. Consult nephrology. Initiate treatment according to guidelines. In case of no improvement or worsening, permanently discontinue ezabenlimab and BI 836880. Ezabenlimab and BI 836880 may only be re-started upon recovery to grade 1 or less, and on corticosteroid ≤ 10 mg per day.
- For Grade 3 or higher nephritis, permanently discontinue ezabenlimab and BI 836880. Consult nephrology. Treat with steroids 1-2 mg/kg prednisone or equivalent. If improved to grade 1 or less, taper corticosteroids over no less than 4-6 weeks.
- Ezabenlimab and BI 836880 should also be permanently discontinued for recurrent nephritis grade 2 or higher.

Rash

- For Grade 1 rash, continue ezabenlimab and BI 836880. Initiate topical treatment.
- For Grade 2 rash, ezabenlimab and BI 836880 may be continued, in case of no improvement upon weekly monitoring, consider interruption of ezabenlimab and BI 836880 therapy. Treat topically, add systemic therapies as clinically appropriate.
- For Grade 3 rash, withhold ezabenlimab and BI 836880. Initiate topical and systemic therapy as per available guidelines. Upon improvement of event to grade 1 or less, and on corticosteroid ≤ 10 mg per day, consult with dermatology whether therapy with ezabenlimab and BI 836880 might be restarted, especially in case no alternative anti-neoplastic therapy is available.
- For Grade 4 rash, ezabenlimab and BI 836880 should be permanently discontinued.

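### In Appendix 10.4, a patient with raised baseline AST/ALT but baseline bilirubin at or below 1.5x ULN meets two different re-exposure rules when immune-related bilirubin rises to >3-5x ULN

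*Protocol*

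**What the plan says.** All of the rules sit in Protocol Appendix 10.4.

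- **Permanent-discontinuation list.** Hepatitis of Grade 3 or higher ends treatment with both drugs. The list spells this out separately for each analyte: "transaminase >5 times ULN [or >10 times ULN if baseline was $>2.5-5$ times ULN" and "total bilirubin >3 times ULN [or >5 times ULN if baseline was $>1.5-3$ times ULN". Each relaxed limit depends on the baseline of the same analyte.
- **Hepatitis section, general line.** "For Grade 3 or higher hepatitis, ezabenlimab and BI 836880 has to be permanently discontinued". The Grade 2 line above it covers AST/ALT 3-5x ULN and bilirubin up to 3x ULN, and calls for suspension.
- **Hepatitis section, elevated-baseline block.** Its heading is "For eligible patients with elevated screening/baseline AST/ALT (>2.5-5x ULN or bilirubin >1.5-3x ULN", so either analyte is enough to enter. The suspend rule is "AST/ALT >2x baseline to ≤10x ULN and/or bilirubin >2x baseline to ≤5x ULN, ezabenlimab and BI 836880 should be suspended". Restart "may be considered upon recovery to baseline or less, and on corticosteroid" at or below 10 mg per day. The permanent stop is "In case of increased AST/ALT >10x ULN and/or bilirubin >5x ULN, ezabenlimab and BI 836880 have to be permanently discontinued".

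Section 3.3.2 (both parts) caps total bilirubin at 1.5x ULN at entry and allows AST/ALT up to 5x ULN in patients with liver metastases. Section 4.1.4 requires any cycle delay to be reported to the Clinical Monitor, and further treatment is decided by the investigator in agreement with that monitor.

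**The concern.** The list ties the 5x ULN bilirubin limit to a raised baseline bilirubin. The block, read as written, gives that limit to everyone who enters it, including a patient who enters on AST/ALT alone. The entry criteria admit exactly that patient: liver metastases, AST/ALT between 2.5x and 5x ULN, bilirubin within 1.5x ULN.

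What is at stake is whether both investigational drugs may be given again after an immune-related bilirubin rise into the >3-5x ULN range. Two investigators could each follow the appendix and reach opposite decisions on re-exposure.

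**Working it through.** No sample size, power or error rate is involved, and the plan gives no figure to reproduce. The check sets the two rules side by side.

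**Inputs.** Let b be baseline bilirubin and x on-treatment bilirubin, both in multiples of ULN. Baseline AST/ALT is >2.5-5x ULN and stays there, so only bilirubin drives the decision.

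- List: permanent stop if x > 3; if 1.5 < b ≤ 3, permanent stop only if x > 5.
- Block: suspend if 2b < x ≤ 5; permanent stop if x > 5.
- Entry (Section 3.3.2): b ≤ 1.5.

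**Step 1.** If b ≤ 1.5, then 2b ≤ 3.0. Any x above 3 is therefore also above 2b, so every x in (3, 5] falls in the block's suspend range while the list requires a permanent stop. The band is 5 - 3 = 2x ULN wide and is the same for every admissible b.

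**Step 2.** Examples with baseline AST 3x ULN:

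| b | 2b | x | List | Block |
|---|---|---|---|---|
| 1.0 | 2.0 | 3.0 | no permanent stop | suspend |
| 1.0 | 2.0 | 4.0 | permanent stop | suspend, restart possible |
| 1.5 | 3.0 | 3.1 | permanent stop | suspend, restart possible |
| 1.0 | 2.0 | 5.0 | permanent stop | suspend, restart possible |
| 1.0 | 2.0 | 5.1 | permanent stop | permanent stop |
| 2.0 | 4.0 | 4.1 | no permanent stop | suspend |
| 2.0 | 4.0 | 5.1 | permanent stop | permanent stop |

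The texts part only above 3x and up to 5x ULN, and only when baseline bilirubin is at or below 1.5x ULN. When baseline bilirubin is >1.5-3x ULN they agree on the permanent stop.

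**Step 3.** Does the general Grade 3 line add a second conflict? Suppose the graded lines still applied to patients in the block. A patient enrolled with AST at 3-5x ULN would then meet the Grade 2 suspend line at baseline, before any change. The separately headed block makes sense only if it replaces the graded lines for these patients. What remains is the list against the block.

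**Step 4.** Reach. The protocol does not report how many patients had this baseline pattern. Section 1.1 gives 44 of 252 treated patients (44/252 = 17.5%) still on treatment in January 2022. That is a loose ceiling on those a later wording change could touch. An affected patient must also have liver metastases, AST/ALT in the raised range, and immune-related bilirubin in the band.

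**The case against.** The best reply is that the block restates the list. Its number pairs are the same (2.5-5x with 10x for AST/ALT, 1.5-3x with 5x for bilirubin), and the list ties each pair to one analyte. Read that way, the difference disappears. The reading is plausible, but the block does not state it. It also has a cost: since entry caps bilirubin at 1.5x ULN, the block's relaxed bilirubin limit would then apply to essentially no patient who met the criteria.

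A second reply is that both texts can be obeyed at once by suspending and never restarting, because the block only permits restart. That is true and it is the cautious course, but it does not tell the investigator which limit governs re-exposure.

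Third, there are controls. Section 4.1.4 brings in the Clinical Monitor after a delayed cycle, and the general text on Grade 3 immune-related events adds: "Expert consultancy is recommended prior to restart of therapy". Appendix 10.4 also describes its own guidance as limited and points to published guidelines. These lower the risk of unsafe re-exposure. None of them chooses between the two limits.

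A reader might infer that the general Grade 3 line is a further contradiction. Step 3 of the working shows why the documents do not support that. A reader might also infer that one text lets dosing continue through bilirubin of 3-5x ULN. Neither does.

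**Conclusion.** The discrepancy is real as worded, and it is minor. For baseline AST/ALT >2.5-5x ULN with baseline bilirubin at or below 1.5x ULN, immune-related bilirubin above 3x and up to 5x ULN is a permanent stop under the list and a suspension with possible restart under the block.

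This rests on reading the block's heading literally and on the event being immune-related. Only re-exposure differs; dosing halts either way. No endpoint or statistical figure changes. The number affected is unknown and probably very small, and the 17.5% should not be taken as an estimate: nothing in the protocol shows that even one patient met this pattern. The protocol also does not show which limit the sponsor intended. The list is the more explicit and the more cautious of the two, which is the reason to follow it.

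**What to change.** In the elevated-baseline block of Appendix 10.4, tie each relaxed limit to its own analyte:

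- the 10x ULN limit for AST/ALT applies only if baseline AST/ALT was >2.5-5x ULN;
- the 5x ULN limit for bilirubin applies only if baseline bilirubin was >1.5-3x ULN;
- otherwise bilirubin above 3x ULN is a permanent stop.

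One added sentence saying that the block replaces the graded hepatitis lines for these patients would remove the remaining doubt.

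The cost is wording only, with no extra patients, visits or tests. Section 8.1 makes amendments subject to ethics committee and competent authority approval, so this can go with the next amendment and does not justify one of its own.
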